4.5 Availability

Commercially available supplies of ibrutinib will be used in this study.

4.6 Agent destruction and return

Not applicable.

4.7 Contraindications

None.

4.8 Drug interactions

Ibrutinib is primarily metabolized by cytochrome P450 enzyme 3A.

CYP3A Inhibitors:

In healthy volunteers, co-administration of ketoconazole, a strong CYP3A inhibitor, increased C_{max} and AUC of ibrutinib by 29- and 24-fold, respectively.⁷² The highest ibrutinib dose evaluated in clinical trials was 12.5 mg/kg (actual doses of 840 – 1400 mg) given for 28 days with single dose AUC values of 1445 ± 869 ng · hr/mL, which is approximately 50% greater than steady state exposures seen at the highest approved dose (560 mg, in mantle cell lymphoma (MCL)). Concomitant administration of ibrutinib with strong or moderate inhibitors of CYP3A should be avoided. For strong CYP3A inhibitors used short-term (e.g., antifungals and antibiotics for 7 days or less, e.g., ketoconazole, itraconazole, voriconazole, posaconazole, clarithromycin, telithromycin), interruption of ibrutinib therapy during the duration of inhibitor use should be considered. Chronic use of strong CYP3A inhibitors should be avoided. If a moderate CYP3A inhibitor must be

used, the dose of ibrutinib should be reduced to 140 mg daily (from the approved dose of 420 mg daily). Patients taking concomitant strong or moderate CYP3A4 inhibitors should be monitored more closely for signs of toxicity. Grapefruit and Seville oranges should be avoided during ibrutinib treatment, as these contain moderate inhibitors of CYP3A.

CYP3A Inducers:

Administration of ibrutinib with rifampin, a strong CYP3A inducer, decreased ibrutinib C_{max} and AUC by approximately 13- and 10-fold, respectively.⁷² Concomitant use of strong CYP3A inducers (e.g., carbamazepine, rifampin, phenytoin and St. John's Wort) should be avoided, and alternative agents with less CYP3A induction considered.

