Ibrutinib is not significantly cleared renally; urinary excretion of metabolites is < 10% of the dose. Creatinine clearance > 25 mL/min had no influence on the exposure to ibrutinib.

There are no data in patients with severe renal impairment (CrCL < 25 mL/min) or in patients on dialysis.

Hepatic Impairment:

Ibrutinib is metabolized in the liver. In a hepatic impairment trial, a single dose of 140 mg of ibrutinib was administered in non-cancer subjects. Ibrutinib AUC increased 2.7-, 8.2- and 9.8-fold, respectively, in subjects with mild (n=6), moderate (n=10) and severe (n=8) hepatic impairment relative to subjects with normal liver function. Ibrutinib C_{max} increased 5.2-, 8.8- and 7.0-fold, respectively, in subjects with mild, moderate and severe hepatic impairment relative to subjects with normal liver function. For patients with mild liver impairment (Child-Pugh class A), the recommended dose is 140 mg daily (one capsule).

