4.9 Warnings and precautions

Hemorrhage:

Fatal bleeding events have occurred in patients treated with ibrutinib. Grade ≥ 3 bleeding events (subdural hematoma, gastrointestinal bleeding, hematuria and post procedural hemorrhage) have occurred in up to 6% of patients. Bleeding events of any grade, including bruising and petechiae, occurred in approximately half of patients treated with ibrutinib. The mechanism for the bleeding events is not well understood. Ibrutinib may increase the risk of hemorrhage in patients receiving antiplatelet or anticoagulant therapies. Based on the risk-benefit ratio, ibrutinib is suggested to be withheld for at least 3 to 7 days pre- and post-surgery depending upon the type of surgery and the risk of bleeding.

Infections:

Fatal and non-fatal infections have occurred with ibrutinib therapy. Grade ≥ 3 infections occurred in 14% to 26% of patients. Cases of progressive multifocal leukoencephalopathy (PML) have occurred in patients treated with ibrutinib. Patients should be monitored for fever and infections and evaluated promptly.

Cytopenias:

Treatment-emergent Grade 3 or 4 cytopenias including neutropenia (range, 19 to 29%), thrombocytopenia (range, 5 to 17%), and anemia (range, 0 to 9%) occurred in patients treated with ibrutinib. Complete blood counts (CBCs) should be monitored monthly.

Atrial Fibrillation:

Atrial fibrillation and atrial flutter (range, 6 to 9%) have occurred in patients treated with ibrutinib, particularly in patients with cardiac risk factors, acute infections, and a previous history of atrial fibrillation. Patients should be clinically monitored periodically for atrial fibrillation. Patients who develop arrhythmic symptoms (e.g., palpitations, lightheadedness) or new onset dyspnea should have an electrocardiogram (ECG) performed. If atrial fibrillation persists, the risks and benefits of treatment and dose modification should be considered.

Second Primary Malignancies:

Other malignancies (range, 5 to 14%) including non-skin carcinomas (range, 1 to 3%) have occurred in patients treated with ibrutinib. The most frequent second primary malignancy was non-melanoma skin cancer (4 to 11 %).

Tumor Lysis Syndrome (TLS):

TLS has been reported with ibrutinib therapy. Patients should be monitored closely and appropriate precautions taken in patients at risk for TLS (e.g. high tumor burden).

Embryo-Fetal Toxicity:

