Based on findings in animals, ibrutinib can cause fetal harm when administered to a pregnant woman. Ibrutinib caused malformations in rats at exposures 14 times those reported in patients with MCL and 20 times those reported in patients with CLL or Waldenstrom's macroglobulinemia (WM), receiving ibrutinib doses of 560 mg per day and 420 mg per day, respectively. Reduced fetal weights were observed at lower exposures. Women should avoid becoming pregnant while taking ibrutinib. If this drug is used during pregnancy or if the patient becomes pregnant while taking this drug, the patient should be apprised of the potential hazard to a fetus.

5 ELIGIBILITY CRITERIA**5.1 Inclusion criteria (all criteria must be met):**

- 5.1.1 Patients with a diagnosis of CLL (any stage) with ALC $\geq 20 \times 10^9/l$, requiring therapy.
 - 5.1.2 Able to receive ibrutinib through commercial supply, i.e., insured patients meeting FDA-approved indications.
 - 5.1.3 Age ≥ 18 years.
 - 5.1.4 Eastern Cooperative Oncology Group (ECOG) performance status of 0-2.
 - 5.1.5 Adequate end organ function, defined as the following: total bilirubin $\leq 1.5 \times$ upper limit of normal (ULN, unless due to Gilbert syndrome, in which case it should be $\leq 3.0 \times$ ULN), ALT and AST $\leq 2.5 \times$ ULN, CrCL ≥ 25 ml/min.
 - 5.1.6 Able to understand and sign the IRB-approved informed consent document for this trial.
 - 5.1.7 Women of childbearing potential (WOCBP) must practice 2 effective methods of birth control during the course of the study. Male patients who are partners of WOCBP should also practice an effective method of contraception. Effective methods of birth control include diaphragm or condoms with spermicidal foam or jelly, birth control pills (BCPs), injections or patches, intra-uterine devices (IUDs) and surgical sterilization.
- Postmenopausal women must be amenorrheic for ≥ 12 months to be considered of non-childbearing potential.
 - Women and men must continue birth control for the duration of the trial and ≥ 3 months after the last dose of study drug.
 - All WOCBP MUST have a negative pregnancy test prior to beginning ibrutinib on study.

5.1.8 Patients should have discontinued any and all other therapy for CLL ≥ 48 hours prior to start of study therapy and recovered from any toxicity due to these therapies to grade ≤ 1 .

5.2 Exclusion criteria:

5.2.1 Previous treatment with ibrutinib.

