5.2.2 Current therapy with warfarin or other anticoagulants at therapeutic doses, e.g., low molecular weight heparin, fondaparinux, dabigatran, rivaroxaban, apixaban or edoxaban that are unable to be discontinued.

5.2.3 Active gastrointestinal conditions that are expected to impair absorption of orally administered medications.

5.2.4 Active, uncontrolled infection.

5.2.5 Inability to understand a written informed consent document.

5.2.6 Pregnancy or lactation.

5.2.7 Patients with leukemic involvement of the central nervous system.

5.2.8 Patients who currently have or have a history of the following within 6 months preceding study entry are not eligible:

- Unstable angina (UA) or myocardial infarction (MI).
- Clinically significant atrial or ventricular arrhythmias (e.g., AF, atrial flutter, ventricular tachycardia, ventricular fibrillation, or *torsades de pointes*).
- New York Heart Association (NYHA) class III or IV heart failure.

5.2.9 Patients on strong CYP3A inducers or inhibitors that are unable to be discontinued. The list of drugs that interact with cytochrome P450 enzymes can be found online at: <http://medicine.iupui.edu/clinpharm/DDIs/ClinicalTable.aspx>

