6.2 Treatment plan

Patients will receive ibrutinib orally daily for 3 cycles. Cycles will be 28 days long. Ibrutinib will be administered continuously, at approximately the same time each day, without regard to food. In the first cycle, the daily dose of ibrutinib will be 420 mg (3 capsules), in the second cycle, 280 mg (2 capsules) and in the third cycle, 140 mg (1 capsule). Patients will swallow the ibrutinib capsules whole with water without opening, breaking or chewing them.

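### Sections 5 and 6 do not carry through the 140 mg daily dose that Section 4 gives for an unavoidable moderate CYP3A inhibitor or for mild liver impairment

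*Combined protocol and SAP*

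**What the plan says.** **Section 4 (drug information).** Section 4.8 states: "Concomitant administration of ibrutinib with strong or moderate inhibitors of CYP3A should be avoided". If a moderate inhibitor is unavoidable, "the dose of ibrutinib should be reduced to 140 mg daily". It adds: "Patients taking concomitant strong or moderate CYP3A4 inhibitors should be monitored more closely for signs of toxicity". The hepatic part of Section 4.4 states: "For patients with mild liver impairment (Child-Pugh class A), the recommended dose is 140 mg daily (one capsule".

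**Eligibility.** Section 5.1.5 begins "Adequate end organ function, defined as the following: total bilirubin" and limits bilirubin to 1.5 × ULN (3.0 × ULN in Gilbert syndrome), ALT and AST to 2.5 × ULN, and creatinine clearance to at least 25 ml/min. It has no Child-Pugh criterion, and Section 5.2 has no hepatic exclusion. The CYP3A exclusion, 5.2.9, reads: "Patients on strong CYP3A inducers or inhibitors that are unable to be discontinued".

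**Treatment.** Section 6.2 says "In the first cycle, the daily dose of ibrutinib will be 420 mg (3 capsules", followed by 280 mg in cycle 2 and 140 mg in cycle 3, with no exception. Section 11 repeats this schedule for all patients. Section 6.3 interrupts or lowers the dose only for toxicity. Section 6.6 prohibits strong CYP3A inhibitors and inducers and is silent on moderate inhibitors. Section 6.7 allows antimicrobials without reference to 6.6.

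**The concern.** Two parts of one protocol give different doses to the same eligible patient. Staff working from Sections 5 and 6 would enrol someone with Child-Pugh A disease, or someone on a moderate inhibitor, and start at 420 mg. Staff working from Section 4 would give 140 mg.

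The first course exposes the patient to more drug than the protocol itself advises, and Section 4.9 lists fatal bleeding and atrial fibrillation among the risks. The second departs from 6.2 without written authority, and the patient yields no 420 or 280 mg data for that period. Section 11 has no rule for samples from either patient, although plasma ibrutinib and BTK occupancy are primary endpoints (Section 1.2.1).

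**Working it through.** **1. The sections side by side**
- Moderate CYP3A inhibitor: 4.8 says avoid, or give 140 mg. Sections 5.2.9 and 6.6 name strong agents only, and 6.2 and 6.3 make no provision.
- Child-Pugh A: 4.4 recommends 140 mg. Sections 5.1.5 and 5.2 do not exclude it, and 6.2 and 6.3 make no provision.
- Strong inhibitors: 4.8 says avoid. This rule is carried into 5.2.9 and 6.6, so the CYP3A gap is confined to moderate inhibitors.

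**2. Size of the dose conflict**
- Cycle 1: 420/140 = 3, or 28 × 3 = 84 capsules against 28.
- Cycle 2: 280/140 = 2, or 28 × 2 = 56 capsules against 28.
- Cycle 3: 140/140 = 1, no conflict.

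**3. Exposure in mild impairment (illustration)**
Inputs: mean steady-state AUC of 680 ng·h/mL (SD 517) at 420 mg and a 2.7-fold AUC increase in mild impairment (both 4.4); mean single-dose AUC of 1445 (SD 869) at the highest dose evaluated (4.8). Assuming exposure is proportional to dose:
- 420 mg: 680 × 2.7 = 1836, and 1836/1445 = 1.27.
- 280 mg: 680 × (280/420) × 2.7 = 1224.
- 140 mg: 680 × (140/420) × 2.7 = 612, close to the usual 680 at 420 mg.

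The Section 4.4 dose therefore makes pharmacological sense. The caveats are real: the 2.7 comes from a single 140 mg dose in non-cancer subjects, six of them with mild impairment, and 1836 lies within one SD of 1445 (1445 + 869 = 2314). For moderate inhibitors the documents give no exposure multiplier, so only the dose ratio can be stated.

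**4. Samples at stake per patient**
By the study calendar and Appendix C, each cycle has five post-dose samples: day 1 at 4 and 24 h, day 8 at 4 and 24 h, and day 28 at 24 h. Cycles 1 and 2 give 2 × 5 = 10. A patient held at 140 mg throughout both cycles supplies none of these at 420 or 280 mg.

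**5. Effect on the occupancy test**
Section 11 uses a one-sample t-test of 95% against 85%. Exact power is P(|T| > t(1 − α/2, n − 1)), where T is noncentral t with n − 1 degrees of freedom and noncentrality √n × 0.10/SD.

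The plan's own figures reproduce:
- SD 0.10, two-sided α 0.05, n = 10: noncentrality 3.162, power 80.3%.
- SD 0.10, two-sided α 0.05, n = 12: noncentrality 3.464, power 88.3%. The plan states 80–88% for n = 10 to 12.
- SD 0.05, two-sided α 0.01, n = 8: noncentrality 5.657, power 95.1%. The plan states 95%.

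The documents do not say how many patients would be lost at a dose level. As an assumed range, at SD 0.10 and α 0.05:
- none lost (n = 12): 88%
- one lost (n = 11): 85%
- two lost (n = 10): 80%
- three lost (n = 9): 75%
- four lost (n = 8): 68%

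Up to two losses stay within the stated range. At the SD of about 5% that Section 11 expects, four losses still leave 95% power even at α 0.01.

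**The case against.** **Section 4.8 is itself protocol text.** A specific rule can be read as qualifying the general schedule in 6.2, which would make the CYP3A half mainly a missing cross-reference. This has some force. But the authors did carry the strong-agent rule into 5.2.9 and 6.6, so silence there on moderate inhibitors can fairly be read as permission. Nothing in the protocol settles the order of precedence.

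**The hepatic text is only a recommended dose**, placed in a pharmacokinetics description and resting on a small single-dose study. That is right, and it should not be called a binding rule. The limits in 5.1.5 narrow who is affected, but they do not exclude Child-Pugh A.

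**There are safeguards.** The calendar records concurrent medications and adverse events throughout, and 6.3 interrupts dosing for grade 3 or higher non-hematologic toxicity. These act after exposure and do not set the starting dose.

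**A stronger reading to resist.** A reader might infer from 6.7, together with the antifungals and antibiotics named in 4.8, that the protocol openly permits moderate inhibitors and that their use is likely. The documents do not support this. Those drugs are listed in 4.8 as strong inhibitors, and 6.6 already prohibits them. The only moderate inhibitors that 4.8 identifies are those in grapefruit and Seville oranges. Nor can the number affected be read from Section 4.9, where grade 3 or higher "infections occurred in 14% to 26% of patients": that counts infections, not inhibitor users.

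**Conclusion.** The point holds as a gap in safety and consistency, and it should be fixed. For an affected patient the scheduled dose is three times the Section 4 dose in cycle 1 and twice in cycle 2. This follows from the text alone. The exposure figures in mild impairment further assume dose proportionality and a ratio from six subjects.

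The number affected among the 12 patients is not given and may be zero. A reader might also infer that the gap undermines the BTK occupancy conclusions. It does not: with one or two patients lost at a dose level, power stays within the plan's own 80–88% at SD 0.10, and it is higher at the SD the plan expects.

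**What to change.** (a) **Section 5.2.9:** exclude patients on strong CYP3A inducers, or on strong or moderate CYP3A inhibitors, that cannot be stopped.

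(b) **Sections 6.6, 6.3, 6.7 and 11:** in 6.6, also prohibit moderate CYP3A inhibitors unless medically unavoidable. In 6.3, state that ibrutinib is then 140 mg daily while the inhibitor is used, returning afterwards to the scheduled dose for that cycle. In 6.7, make antimicrobials subject to 6.6. In Section 11, state that samples taken at a reduced dose do not count toward the 420 or 280 mg analysis.

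(c) **Section 5.2:** exclude known hepatic impairment (Child-Pugh class A or worse), judged from the history and the laboratory tests already listed in Section 7. State that isolated Gilbert syndrome is not impairment, since 5.1.5 admits it, and that no new clotting test is required, since 7.2 lists none.

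**Cost:** wording only, with no added visit or test and one sentence on analysis. History, concomitant medications, albumin and bilirubin are already collected at screening. A few candidates become ineligible. Because the hepatic criterion relies on known disease and existing tests, it may miss an unrecognised case.

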4.9 Warnings and precautions

Hemorrhage:

Fatal bleeding events have occurred in patients treated with ibrutinib. Grade ≥ 3 bleeding events (subdural hematoma, gastrointestinal bleeding, hematuria and post procedural hemorrhage) have occurred in up to 6% of patients. Bleeding events of any grade, including bruising and petechiae, occurred in approximately half of patients treated with ibrutinib. The mechanism for the bleeding events is not well understood. Ibrutinib may increase the risk of hemorrhage in patients receiving antiplatelet or anticoagulant therapies. Based on the risk-benefit ratio, ibrutinib is suggested to be withheld for at least 3 to 7 days pre- and post-surgery depending upon the type of surgery and the risk of bleeding.

Infections:

Fatal and non-fatal infections have occurred with ibrutinib therapy. Grade ≥ 3 infections occurred in 14% to 26% of patients. Cases of progressive multifocal leukoencephalopathy (PML) have occurred in patients treated with ibrutinib. Patients should be monitored for fever and infections and evaluated promptly.

Cytopenias:

Treatment-emergent Grade 3 or 4 cytopenias including neutropenia (range, 19 to 29%), thrombocytopenia (range, 5 to 17%), and anemia (range, 0 to 9%) occurred in patients treated with ibrutinib. Complete blood counts (CBCs) should be monitored monthly.

Atrial Fibrillation:

Atrial fibrillation and atrial flutter (range, 6 to 9%) have occurred in patients treated with ibrutinib, particularly in patients with cardiac risk factors, acute infections, and a previous history of atrial fibrillation. Patients should be clinically monitored periodically for atrial fibrillation. Patients who develop arrhythmic symptoms (e.g., palpitations, lightheadedness) or new onset dyspnea should have an electrocardiogram (ECG) performed. If atrial fibrillation persists, the risks and benefits of treatment and dose modification should be considered.

Second Primary Malignancies:

Other malignancies (range, 5 to 14%) including non-skin carcinomas (range, 1 to 3%) have occurred in patients treated with ibrutinib. The most frequent second primary malignancy was non-melanoma skin cancer (4 to 11 %).

Tumor Lysis Syndrome (TLS):

TLS has been reported with ibrutinib therapy. Patients should be monitored closely and appropriate precautions taken in patients at risk for TLS (e.g. high tumor burden).

Embryo-Fetal Toxicity:

Based on findings in animals, ibrutinib can cause fetal harm when administered to a pregnant woman. Ibrutinib caused malformations in rats at exposures 14 times those reported in patients with MCL and 20 times those reported in patients with CLL or Waldenstrom's macroglobulinemia (WM), receiving ibrutinib doses of 560 mg per day and 420 mg per day, respectively. Reduced fetal weights were observed at lower exposures. Women should avoid becoming pregnant while taking ibrutinib. If this drug is used during pregnancy or if the patient becomes pregnant while taking this drug, the patient should be apprised of the potential hazard to a fetus.

5 ELIGIBILITY CRITERIA**5.1 Inclusion criteria (all criteria must be met):**

- 5.1.1 Patients with a diagnosis of CLL (any stage) with ALC $\geq 20 \times 10^9/l$, requiring therapy.
 - 5.1.2 Able to receive ibrutinib through commercial supply, i.e., insured patients meeting FDA-approved indications.
 - 5.1.3 Age ≥ 18 years.
 - 5.1.4 Eastern Cooperative Oncology Group (ECOG) performance status of 0-2.
 - 5.1.5 Adequate end organ function, defined as the following: total bilirubin $\leq 1.5 \times$ upper limit of normal (ULN, unless due to Gilbert syndrome, in which case it should be $\leq 3.0 \times$ ULN), ALT and AST $\leq 2.5 \times$ ULN, CrCL ≥ 25 ml/min.
 - 5.1.6 Able to understand and sign the IRB-approved informed consent document for this trial.
 - 5.1.7 Women of childbearing potential (WOCBP) must practice 2 effective methods of birth control during the course of the study. Male patients who are partners of WOCBP should also practice an effective method of contraception. Effective methods of birth control include diaphragm or condoms with spermicidal foam or jelly, birth control pills (BCPs), injections or patches, intra-uterine devices (IUDs) and surgical sterilization.
- Postmenopausal women must be amenorrheic for ≥ 12 months to be considered of non-childbearing potential.
 - Women and men must continue birth control for the duration of the trial and ≥ 3 months after the last dose of study drug.
 - All WOCBP MUST have a negative pregnancy test prior to beginning ibrutinib on study.

5.1.8 Patients should have discontinued any and all other therapy for CLL ≥ 48 hours prior to start of study therapy and recovered from any toxicity due to these therapies to grade ≤ 1 .

5.2 Exclusion criteria:

5.2.1 Previous treatment with ibrutinib.

5.2.2 Current therapy with warfarin or other anticoagulants at therapeutic doses, e.g., low molecular weight heparin, fondaparinux, dabigatran, rivaroxaban, apixaban or edoxaban that are unable to be discontinued.

5.2.3 Active gastrointestinal conditions that are expected to impair absorption of orally administered medications.

5.2.4 Active, uncontrolled infection.

5.2.5 Inability to understand a written informed consent document.

5.2.6 Pregnancy or lactation.

5.2.7 Patients with leukemic involvement of the central nervous system.

5.2.8 Patients who currently have or have a history of the following within 6 months preceding study entry are not eligible:

- Unstable angina (UA) or myocardial infarction (MI).
- Clinically significant atrial or ventricular arrhythmias (e.g., AF, atrial flutter, ventricular tachycardia, ventricular fibrillation, or *torsades de pointes*).
- New York Heart Association (NYHA) class III or IV heart failure.

5.2.9 Patients on strong CYP3A inducers or inhibitors that are unable to be discontinued. The list of drugs that interact with cytochrome P450 enzymes can be found online at: <http://medicine.iupui.edu/clinpharm/DDIs/ClinicalTable.aspx>

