2.2 Ibrutinib mechanism of action and preclinical data in CLL

B-cell receptor (BCR) signaling plays a key role in CLL pathogenesis, and BTK has a critical role in BCR signaling in both normal and malignant B-cells.^{7,8} BTK is important for antigen-induced BCR activation in both normal, mature B-cells and in CLL and mediates survival and proliferation via amplification of downstream effector pathways, e.g., phosphatidylinositol 3-kinase/Akt (PI3K/Akt), mitogen activated protein kinase/extracellular signal-regulated kinase (MAPK/ERK) and nuclear factor kappa B (NF- κ B).^{7,8} Additionally, autonomous BCR signaling has also been described in CLL, which is not, however, associated with activating mutations in any of the BCR components.⁸

Ibrutinib inactivates BTK through irreversible, covalent bonding to the Cys481 residue in the adenosine triphosphate (ATP)-binding domain of BTK.⁹ BTK has been shown to be critical for the development and expansion of CLL and an important target of ibrutinib.¹⁰ Indeed, BTK point mutations (C481S) that convert ibrutinib to a reversible inhibitor, as well as activating mutations in phospholipase C gamma 2 (PLC γ 2), located immediately downstream of BTK, have been implicated in the pathogenesis of acquired resistance to ibrutinib in CLL.¹¹ The success of the more selective BTK inhibitor, acalabrutinib, in heavily pretreated

patients with CLL, further testifies to the relevance of BTK as a major therapeutic target in this disease.¹²

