3. RATIONALE FOR STUDYING DIFFERENT DOSES OF IBRUTINIB IN PATIENTS WITH CLL

Dose of ibrutinib versus clinical response

In a phase I study of ibrutinib in 56 patients with relapsed or refractory B-cell malignancies, BTK occupancy $\geq 95\%$ was achieved 4 hours post-dose in all patients receiving 2.5 mg/kg/day.⁶⁰ Additionally, complete or near-complete BTK occupancy was observed in patients with area under the curve (AUC) exceeding 160 ng x h/ml.⁶⁰ BTK occupancy was measured using a highly specific fluorescent affinity probe, whose binding to the BTK active site had previously been shown to tightly correlate with blockade of BCR signaling and in vivo efficacy.⁹ Dose escalation proceeded up to three dose levels above the level at which full BTK occupancy was observed, i.e., 12.5 mg/kg/day, and all dosing cohorts from 2.5 through 12.5 mg/kg/day had $>95\%$ BTK occupancy and similar response rates.⁶⁰ In the context of clinical observations in patients with CLL that show that patients whose ibrutinib

dose is reduced to 280 mg/d or 140 mg/d because of AEs continue to respond ([name], unpublished observations), these data provide a compelling argument that doses of ibrutinib lower than the approved 420 mg/d will be effective in CLL.

Decrease in off-target effects

Lower doses should result in lower concentrations of free drug in plasma and reduced binding to off-target kinases such as TEC, likely leading to a decreased incidence of AEs such as AF and bleeding manifestations. Acalabrutinib, a new and more selective irreversible BTK inhibitor, does not inhibit other kinases such as EGFR, TEC and ITK at pharmacologically active concentrations.¹² In a phase I/II trial in 61 heavily pretreated patients (median 3 prior therapies, 31% with del17p, 75% with unmutated IgVH), acalabrutinib produced an ORR of 95% (85% PRs, 10% PR-Ls, 100% ORR in patients with del17p) without any major hemorrhage or AF.¹²

Decrease of total BTK in CLL cells during ibrutinib therapy

Prior investigations in murine models demonstrated that BTK protein total levels increased after B-cell receptor pathway stimulation.⁶¹ Similar observations were recently made in an adoptive transfer CLL murine model.⁶² The mechanism involved the CXCR4-CXCL12 signaling pathway. As a corollary, inhibition of BTK by ibrutinib in murine model resulted in a decline in total BTK along with internalization of CXCR4 receptors.

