11 STATISTICAL CONSIDERATIONS

Ibrutinib is an inhibitor of Bruton's tyrosine kinase (BTK). The FDA has approved it for relapsed patients with CLL and frontline patients with del17p. Its standard dose is 420 mg/day (three 140-mg capsules). The primary objective of this pilot study is to determine the effects of different daily doses of ibrutinib (420 mg, 280 mg, 140 mg) on free drug levels in plasma, BTK occupancy by ibrutinib, BTK mRNA, BTK phospho- and total protein levels and NF- κ B activity. In total, 12 patients will be enrolled in this study. All patients will receive ibrutinib orally daily for 3 cycles. Each cycle will be 28 days long. In the first cycle, the daily dose of ibrutinib will be 420 mg (3 capsules), in the second cycle, 280 mg (2 capsules) and in the third cycle, 140 mg (1 capsule). That is, each patient will go through the three cycles with decreasing dose levels as described above. The half-life of ibrutinib is 4 to 6 hours and the drug does not accumulate after repeated oral dosing. Therefore, the influence of a previous cycle on the subsequent cycle is minimal.

Among the above pharmacokinetic and pharmacodynamic (PK/PD) parameters, a key factor is BTK occupancy. A dose level with BTK occupancy by ibrutinib $\geq 95\%$ (alternative hypothesis, H1) is regarded as sufficient, and that with an occupancy rate $< 85\%$ (null hypothesis, H0) is insufficient. Using a t-test to test H0 vs. H1, when the standard deviation of BTK occupancy rate (used as a continuous variable) is 0.10, a sample size of 10 to 12 patients can provide 80-88% power, at 2-sided significance level 0.05. This t-test will be conducted for each dose level. The data set described below shows that the standard deviation of BTK occupancy rate is about 5% when its mean is higher than 85%. As such, a sample size of 8 can provide 95% power at significance level 0.01. Therefore, even considering multiple testing adjusted by the Bonferroni method, and sample size reduction due to various reasons, this trial will still have sufficient power. An ideal dose level is sufficiently high to provide a high ($\geq 95\%$) BTK occupancy level by ibrutinib, but not higher, so that there is not much “left over drug” in plasma to cause toxicities, i.e, a low free drug level in plasma is desirable.

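### Section 5.2.1 excludes only prior ibrutinib, so a patient treated with another irreversible BTK inhibitor can enter and may lack an untreated day 1 baseline

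*Combined protocol and SAP*

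**What the plan says.** Section 5.2.1 excludes "Previous treatment with ibrutinib" and no other BTK inhibitor. Section 5.1.8 reads "Patients should have discontinued any and all other therapy for CLL ≥ 48 hours prior to start of study therapy", and adds that toxicity from that therapy must have recovered to grade 1 or less. Section 5.1.2 limits entry to "insured patients meeting FDA-approved indications". Section 11 counts relapsed CLL among those indications, so 5.1.2 does not screen out a patient who relapsed on a different BTK inhibitor. Nothing else in 5.1 or 5.2 does so either, and the pretreatment work-up in section 7 includes no BTK mutation test.

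The protocol is aware of both relevant facts. Section 3 describes acalabrutinib as "a new and more selective irreversible BTK inhibitor" and cites a phase I/II trial of it in 61 heavily pretreated CLL patients. Section 2.2 refers to "BTK point mutations (C481S) that convert ibrutinib to a reversible inhibitor" and links them to acquired resistance to ibrutinib.

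Section 1.2.1 makes day 1 the baseline for the primary endpoints, which include BTK occupancy, BTK mRNA, phospho- and total BTK protein, downstream signaling, chemokines and NF-κB. Section 8.7 and Appendix C provide a pre-dose occupancy sample, but no rule uses it to exclude a patient or adjust the analysis. Section 11 tests occupancy at each dose with a t-test in 12 patients, taking below 85% as insufficient and 95% or more as sufficient. Each patient takes 420, 280 and 140 mg in turn.

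**The concern.** The prior-ibrutinib exclusion has the effect of giving every patient an untreated BTK system on day 1. Another covalent inhibitor could defeat that in the same way, and 48 hours off treatment may not restore the baseline. Section 3 argues that BTK inhibition by ibrutinib lowers total BTK protein. If another irreversible inhibitor acts similarly, the day 1 values for BTK protein and the measures downstream of it would be treated values, and change from day 1 would understate the drug's effect in that patient.

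The occupancy test raises a second question. With 12 patients, no robust method and no outlier rule, can one such patient change the conclusion? The answer depends on direction. Residual binding would raise the reading, whereas resistant BTK would lower it. The two cases need separate checks.

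**Working it through.** **Inputs.** From section 11: null mean 0.85, alternative 0.95, SD 0.10 for planning and about 0.05 from earlier data, n = 10 to 12, two-sided alpha 0.05, one test per dose (three tests). The occupancy of a previously treated patient is not in the documents, so it is an assumption and is varied.

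**The plan's own power.** One-sample t-test, noncentrality = (0.95 − 0.85)/SD × √n, n − 1 degrees of freedom:
- SD 0.10, alpha 0.05: n = 10 gives 80.3%, n = 11 gives 84.8%, n = 12 gives 88.3%. The stated range of 80-88% is reproduced.
- SD 0.05, n = 8, alpha 0.01: 95.1%. The stated 95% is reproduced.

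**Case A: residual occupancy (reading too high).** One patient is fixed at 1.00 and the other 11 are drawn from a normal distribution (200,000 simulated trials, n = 12, rejection in the upper tail at two-sided 0.05).
- Others' true mean 0.95, SD 0.10: power rises from 88.4% to 91.9%.
- Others' true mean 0.85: the chance of wrongly calling the dose sufficient rises from 2.5% to 4.3% (SD 0.05) or 5.0% (SD 0.10).
- Others' true mean 0.80: that chance stays below 0.1%.

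The 280 and 140 mg tests follow 28 days at 420 mg, so occupancy left by an earlier drug has little bearing on them. What remains is mainly an early cycle 1 matter.

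**Case B: resistant BTK (reading too low), by assumption.** Let the other 11 have sample mean 0.95 and sample SD 0.05, and let one patient be at x:
- mean = (11 × 0.95 + x)/12
- SD² = [10 × 0.05² + (11/12)(0.95 − x)²]/11
- t = (mean − 0.85)/(SD/√12), critical value 2.201

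At x = 0.60: mean = 11.05/12 = 0.921; SD² = (0.0250 + 0.1123)/11 = 0.01248, so SD = 0.112; t = 0.0708/0.0323 = 2.20, p = 0.0504. This is the tipping point. It moves to about 0.665 with Bonferroni (0.05/3 = 0.0167), and to about 0.735 with 8 patients at alpha 0.05.

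Simulated power, n = 12, alpha 0.05, others normal with mean 0.95:

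| One patient at | SD 0.05 | SD 0.10 |
|---|---|---|
| no such patient | about 100% | 88% |
| 0.85 | about 100% | 84.5% |
| 0.70 | 97.6% | 56.3% |
| 0.50 | 1.3% | 5.1% |
| 0.30 | 0% | 0% |

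The inflated SD does most of the damage. Even at x = 0 the mean is 10.45/12 = 0.871, still above 0.85.

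For scale, suppose mutant BTK reads as unoccupied and the rest is 95% occupied. A reading of 0.60 then needs a mutant share m with 0.95(1 − m) = 0.60, so m is about 37%.

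**Scaling.** The documents do not say how occupancy is normalised. If it is scaled to the patient's pre-dose free-BTK signal, a patient with fraction f already bound and true occupancy 0.95 would read 1 − 0.05/(1 − f). That reaches 0.60 at f = 1 − 0.05/0.40 = 0.875.

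**The case against.** A reader might infer that a patient with pre-occupied BTK could overturn the occupancy result. The documents do not support that. The test is against a fixed 85%, residual binding raises the reading, and Case A shows power going up. The exception is normalisation to the pre-dose signal, which the documents neither state nor rule out. The pre-dose sample would also make residual binding visible, although no rule says what to do with it.

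A reader might also infer that the protocol links acalabrutinib to C481S. It does not. Section 2.2 ties the mutation to ibrutinib resistance, and patients with prior ibrutinib are already excluded. That another inhibitor can leave the same resistance is an assumption.

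Nor do the documents show acalabrutinib in general use. Section 3 calls it new and cites only a phase I/II trial. Any such patient must also qualify for commercial ibrutinib and have ALC of at least 20 × 10⁹/l. The exposed pool may be very small.

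Finally, section 11 allows summaries by mean (SD) and/or median (range). If the median and range are reported, a single low value would be visible and would barely move the median. The error in Case B would also be toward calling an adequate dose unproven.

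All of these points stand. They limit the size and likelihood of the problem, but they do not close the eligibility gap or restore a missing day 1 baseline.

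**Conclusion.** The gap in eligibility is real on the text. Its firmest consequence is that a patient recently treated with another irreversible BTK inhibitor may have no untreated day 1 baseline for the primary endpoints.

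For the occupancy test, residual binding is a minor upward bias: a false-sufficient rate of about 4-5% instead of 2.5% when the true mean of the others sits exactly at 85%, and less when it is lower. The serious effect is conditional. It requires a patient with resistant BTK at or below about 60% occupancy (others averaging 95%, SD 5%, n = 12), and it rests on an assumption about the other inhibitor that the documents do not make. Because every patient takes all three doses, a reading that low throughout would affect all three tests together. A moderately low value does much less harm: at 70%, power is about 98% with SD 0.05 and 56% with SD 0.10.

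The probability of enrolling such a patient is not given and is probably low. This is a cheap improvement to the plan, not a flaw that threatens it.

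**What to change.** Extend section 5.2.1 so that "Previous treatment with ibrutinib" continues with the words: or any other irreversible (covalent) BTK inhibitor. This closes both routes at once and needs no change to the sample size, sampling schedule or test. The cost is one phrase in the eligibility criteria and the loss of a few otherwise eligible patients.

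If the sponsor prefers to keep such patients eligible, the alternative is to state in section 11, before any data are seen, how the pre-dose occupancy sample will be used to exclude a patient from the occupancy test or adjust for residual binding, and to add a robust sensitivity analysis.
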